#### 1 INTRODUCTION

### 1.1 Background

#### Introduction

New approaches to treatment of Alzheimer's disease (AD) are desperately needed. There are 850,000 people living with dementia in the UK and this is set to increase as the population ages. Annual financial costs exceed £36 billion in UK alone and dementia is the most feared condition of old age. Dementia Roadmap, James Lind Alliance and Lancet Commission prioritise effective routes to timely diagnosis and interventions to help people retain independence and quality of life.

AD pathology accrues over 2-3 decades before diagnosis – with amyloid beta (abeta) plaques emerging very early and then tau deposition detected later (but still before clinical symptoms). There are no licensed treatments for AD that can delay progression although one anti-amyloid therapy has recently been approved by the Food and Drug Administration review and is under NICE review after one of two phase III trials suggested modest benefit in early symptomatic AD.

Through targeting therapy early in the course of disease before symptoms interfere with day-to-day life, we could alter the trajectory of cognitive decline and slow progression to AD dementia. Economic modelling suggests that delaying progression between the prodromal phase of AD, Mild Cognitive Impairment (MCI), and AD dementia by 3 years would reduce the number of cases in the UK by 394000 (as dementia often occurs in the last few years of life) with estimated annual cost saving of £12.7billion.

Modifying sleep quality is an untapped opportunity with potential to delay progression of neurodegenerative diseases such as AD [1] while promoting physiological processes that improve cognition, mental health and wellbeing. There is a multidimensional relationship between sleep disturbance and AD progression [2-4]. Poor sleep is associated with increased likelihood of future dementia [2], AD worsens sleep and poor sleep is linked to worse cognition [5]. Deficits in non-REM (slow wave) sleep [6] have been associated with the degree of abeta and tau burden prior to AD onset as well as memory impairments [7, 8]. Treating sleep might therefore help slow AD progression and improve symptoms of memory loss.

The programme of work here will deliver feasibility, acceptability and diagnostic sensitivity data for home high density overnight EEG and blood biomarkers that will be translated directly into clinical trials to delay progression of Alzheimer's and improve independence and quality of life in older people at risk of AD.

#### Link between sleep macro and microarchitecture and AD

Sleep and circadian rhythm disturbance are well recognised in both AD and MCI with over 60% of memory clinic attendees experiencing at least one recognised sleep disorder such as sleep apnoea or insomnia [9-12]. There are a broad range of sleep abnormalities found in individuals with AD including insomnia, excessive daytime sleepiness and 'sundowning'.

SleepAD Protocol v6.0 6th September 2024

Decreased sleep efficiency, increased duration of stage 1 sleep and an increase in sleep fragmentation compared to age-matched people without dementia is also seen. Circadian rhythm disorders, contributing to sleep disturbance are also generally more marked than in healthy ageing.

While it seems very likely that sleep disturbance results from the pathological cascade underlying AD, more recent data also points to sleep abnormalities themselves causing or exacerbating both cognitive impairment and pathological progression of AD. Toxic breakdown products (including amyloid) are removed via the glymphatic system in mice only during slow wave sleep (SWS). A single night of SWS deprivation has been shown to increase cerebrospinal fluid (CSF) amyloid beta 42 levels in healthy adults[13], and individuals with more severe obstructive sleep apnoea (OSA) have shown increased brain amyloid burden [14]. Furthermore SWS at baseline predicts accumulation of toxic proteins that cause AD in future years [15-17]. Alongside biomarkers, sleep has also been shown to be disrupted long before the onset of symptomatic AD dementia [2, 3]. Therefore, poor sleep might cause or exacerbate pathological changes of AD through failure to remove amyloid and consequent accumulation in turn worsening cognition. Therefore, modifying sleep represents an untapped opportunity with potential to delay progression of neurodegenerative diseases such as AD while promoting physiological processes that improve cognition (particularly long-term memory consolidation), general health and wellbeing. Furthermore, its presence prior to onset of clinical symptoms, may provide an ideal means by which to identify those at highest risk. Early identification is potentially crucial in the future when further therapeutic modalities may be available to alter the pathological disease course.

Microarchitectural features of sleep including the slow oscillations in SWS are causally linked to AD. There are potential treatments to augment SWS. As an example, we have recently shown that a cheap, safe and widely available medication, levodopa, prolongs slow wave sleep (deep, non-REM sleep). Physiological processes during non-REM sleep help to remove pathological proteins that are associated with AD – abeta42 and phosphorylated tau. Therefore prolonging non-REM sleep offers the potential to delay progression of Alzheimer's. There are other emerging interventions to modify sleep being developed by other research groups such as auditory stimulation during non-REM and medications such as zolpidem. For any of these to be rolled out into clinical trials, we need to be able to treat patients for AD when symptoms are mild, and test patients' sleep in their homes.

But, we cannot detect these without EEG measurement (data under review), and there is no standardised way to measure sleep in MCI and AD [18]. EEG has not been implemented at scale in dementia trials and the best system to capture EEG in clinical trials is not established. Therefore we test here home EEG using a set-up as close as possible to in-lab polysomnography but reducing the need for participant travel and overnight stays. We will test the feasibility of this approach alongside memory test testing that would typically be required as part of a clinical trial. In addition, as we know the prevalence of OSA can be high in this population and that this impacts on sleep, we will also monitor for OSA.

### Why measure blood biomarkers

Alzheimer's Disease (AD) is currently not diagnosed sufficiently early for effective treatment. Earlier intervention in AD is crucial, to avert accumulation of AD pathology that begins 20

SleepAD Protocol v6.0 6th September 2024

years before clinical dementia diagnosis, and to prevent distress from delayed diagnosis. Novel AD blood biomarkers identify early AD in research settings [19]

People with Mild Cognitive Impairment (MCI) or early AD dementia could benefit from lifestyle interventions and/or the trial pipeline of disease-modifying drugs [20] but most people (c. 567k people in UK currently) with AD are not diagnosed until they have overt dementia. Moreover, early robust reassurance, using molecular diagnostics, for people with cognitive symptoms but without neurodegenerative disease or dementia could avoid extensive unnecessary testing and reduce distress from diagnostic uncertainty.

Blood levels of phospho-tau (P-tau, marker of tau leakage due to abeta42 oligomeric toxicity) and neurofilament light chain (NFL, marker of all-cause neurodegeneration) are recently validated measures of AD pathology and neurodegeneration respectively that are ready for real-world testing [21]. SIMOA (Single Molecular Array) technology is just now available in UCL employing validated assays of NFL, P-tau-181 and P-tau-217.

Blood biomarkers will support accurate classification at the initial presentation, reduce unnecessary tests and evaluation, enable treatment for conditions which can masquerade as dementia, such as depression, facilitate post-diagnostic support, and therefore support maintaining independence. Potential therapies target specific stages of Alzheimer's disease, with many designed for and tested in early AD dementia and/or MCI due to AD. Dementia services will need to stratify patients according to molecular pathology of AD and disease stage to deliver treatments, but this is not available across the UK in an equitable or affordable way, and in many countries is not accessible at all. If as accurate as expected, acceptable and cost-effective, blood biomarkers can be widely used clinically.

There is less known about blood biomarkers in Lewy body diseases. However, post mortem studies predict that around 50% of people with Lewy Body Dementia will have evidence of Alzhiemer's pathology too [22]. People with dual AD and Lewy body pathology decline faster. Therefore, identifying AD pathology in Lewy body diseases is likely to be of prognostic significance.

#### Accuracy

For people with Mild AD dementia or MCI due to AD reference ranges are available from research cohorts and P-tau 181 alone has an Area Under Receiver Operating Characteristic curve (AUROC) of 0.80 compared to amyloid PET [23] and the combination of NFL and P-tau 181 has an AUROC of 0.88 compared to delayed verification of AD (sensitivity 83-88%, specificity 82-83%) to identify people who have progressive AD pathology as a cause of their MCI at baseline. Simple cognitive tests carried out in clinic such as the Montreal Cognitive Assessment have 90% and 100% sensitivity for MCI and mild AD dementia respectively, with specificity varying according to the cohort (up to 87% when comparing to healthy control in a research cohort) [24]. For people without AD – cerebrospinal fluid (CSF) biomarkers have a very high negative predictive value (94% on a real-world sample after median 4.7 years follow-up). Modelling suggests that combining blood biomarkers with simple cognitive tests will be more sensitive and specific than either test alone.

SleepAD Protocol v6.0 6th September 2024

As blood biomarkers make large scale interventional studies possible in AD at vastly reduced expense (as we can avoid CSF testing or PET scanning), new therapeutic targets for intervention can be tested more rapidly.

The value of blood biomarkers is ultimately determined by the accuracy with which they can predict future AD, and therefore collecting longitudinal data is essential, with progression from MCI to AD as the key outcome of interest. To this end, our pre-clinical/MCI cohort will be followed up at 2 and 5 years after their involvement in the study, to check whether their diagnosis has converted to AD or another dementia. Diagnostic accuracies of all included biomarkers will be assessed, and we will use modelling to examine how specific biomarkers improve dementia risk prediction when combined with baseline demographic and clinical information.

Molecular classification of AD is important alongside exploration of sleep as several studies have suggested distinct interaction between different underlying AD pathology (amyloid, tau or other) and different sleep metrics e.g. [17, 25]. Only by deep characterisation of sleep phenotype as in SleepAD, can we develop clinical trials that target the right sleep treatment to the right patient.

### APOE genotyping

Apolipoprotein E (*APOE*) is a susceptibility gene for late onset AD. The *APOE* £2 allele is protective and the £3 allele is neutral, but the £4 allele increases the carrier's lifetime risk of developing AD. Increasing allele dose is positively associated with AD risk, in a Caucasian sample *APOE* £4 heterozygosity conferred an odds ratio of approximately 3, and £4 homozygosity an odds ratio of approximately 14 [26]. *APOE* £4 is known to have a number of neurophysiological effects decades prior to clinical signs emerge. For £4 carriers these include disrupted resting state brain activity, changes in brain structure, and impact on brain function [27]. Furthermore, *APOE* £4 has been linked with sleep disturbance in healthy older adults, and increased risks of insomnia and obstructive sleep apnoea [28, 29]. Total time spent in SWS was found to be significantly altered in older male £4 homozygotic *APOE* carriers [30]. *APOE* £4 may act as a mediator of the relationship between cognitive decline and sleep, independent of AD pathological change [31]. Of note, sleep has also been shown to modify the relationship between *APOE* £4 and AD, which indicated that sleep consolidation may provide some protection [32]. It would clearly be of great interest to further examine the associations between *APOE* £4, sleep and cognitive decline.

APOE £4 carrier status is also an important factor when evaluating AD risk. In a large prospective longitudinal study (BALTAZAR), baseline plasma p-tau 181 combined with APOE £4 carrier status (plus age, sex and cognitive screening test score) was found to improve the model's predictive performance for conversion from MCI to AD [33]. In a recent prognostic study of preclinical AD cohorts, the combination of APOE4 status and plasma P-tau 217 biomarkers was optimal for predicting longitudinal cognitive decline [34]. In another prognostic study of preclinical AD cohorts using progression to AD as the outcome, plasma P-tau in combination with brief cognitive tests and APOE genotyping significantly improved prediction accuracy [35]. In sum, combining blood biomarkers with APOE4 carrier status and simple cognitive tests, will likely be more sensitive and specific than a single test alone.

SleepAD Protocol v6.0 6th September 2024

We therefore include *APOE* genotyping within the SleepAD study. Determining *APOE* £4 carrier status will further enhance deep characterisation of our sample, and enable us to examine links between £4 carrier status, sleep phenotype, and the presence of positive biomarkers within a real world clinical population.

### Orexin as a biomarker

Orexins are neuropeptides produced in the hypothalamus that play a critical role in maintaining wakefulness [36]. Discovered in 1997, orexin A and orexin B bind to two G-protein-coupled receptors [37]. Their dysfunction is implicated in conditions such as narcolepsy, where deficient orexin production leads to excessive daytime sleepiness and cataplexy [38].

Emerging evidence suggests that orexins are also involved in the pathophysiology of AD, particularly in relation to sleep disturbances and cognitive decline. Abnormal CSF orexin levels have been observed in both transgenic mouse models of AD [39], and in humans with AD pathology [40], where these levels are associated with disruptions in sleep architecture and alterations in biomarkers of Alzheimer's disease.

In cognitively healthy individuals, sleep deprivation has been linked to increased levels of amyloid-beta and phosphorylated tau in the brain and CSF [41, 42], reflecting changes seen in AD [43]. Additionally, orexin levels have been correlated with p-tau in patients with AD [44], suggesting a potential role in the phosphorylation of tau proteins and the progression of AD pathology.

Adding further weight to a role for orexins in AD pathology, dual orexin receptor antagonists (DORAs) have shown promise in improving sleep parameters in this population, particularly in individuals with a mini mental state exam concordant with a diagnosis of MCI [45].

The efficacy of DORAs appears to be circadian-dependent, with administration timed to circadian cycles being crucial for optimal cognitive outcomes [46-48]. Mice with transgenic predisposition to AD pathology administered orexin antagonists at the start of a dark cycle had aggravated pathology [47], in comparison to mice administered orexin antagonists at the end who had ameliorated cognition [48]. This suggests that monitoring orexin levels and accounting for the point in the circadian cycle they were taken could be vital in understanding and optimizing the therapeutic effects of DORAs.

The effect on cognition of DORAs appears to be related to their effect on the quantity of pathogenic proteins in CSF. A small randomized controlled trial (RCT) demonstrated that suvorexant, a DORA, significantly reduced the ratio of phospho-tau 181 to total tau in cognitively unimpaired individuals [46]. Similar effects were observed on CSF amyloid-beta levels in this study, indicating that orexin may directly influence tau phosphorylation and amyloid aggregation, key processes contributing to neuronal and synapse loss in AD.

While CSF orexin appears to have a significant relationship with cognition, this does not appear to be the case with plasma orexin (which does not undergo circadian variability, although this has always been assumed to be insignificant) [49]. Indeed, the only current literature in MCI relates to a methodologically flawed study that found a positive association between constipation and orexin in MCI [50]. Regardless, it may be a helpful comparator because it may provide a baseline value by which to compare CSF level.

SleepAD Protocol v6.0 6th September 2024

Measuring orexin levels in plasma and CSF could therefore provide valuable insights into the degree of sleep-wake cycle and circadian rhythm impairments in patients across the AD pathology spectrum. This approach could serve as a less cumbersome alternative to polysomnography for assessing these disturbances and offer a target for evaluating the effects of orexin antagonists.

Notably, no study to date has examined the relative levels of plasma and CSF orexin, or their relationship to plasma biomarkers of Alzheimer's disease. This is what we propose to do in this protocol amendment. This may provide additional diagnostic clarity about stage of AD, and a potential way to monitor response to DORAs in future clinical trials. Furthermore, it will enable us to better understand the links between sleep characteristics and the presence of positive AD biomarkers within a real-world clinical population.

### 1.2 Rationale For Study Programme

Enhancing sleep holds great promise to improve brain health in later life. Our overarching goal is to improve identification and treatment of disease-related sleep and memory impairment in MCI and AD.

This study programme has two simple major themes, united by the need for sleep and molecular diagnostic data collection in people with early AD. The work is funded by Rosetrees charity to develop feasibility data to enable future large scale roll out of sleep intervention trials in people with early accurate molecular diagnosis of AD.

#### **2 STUDY OBJECTIVES**

### 2.1 Objectives

#### 2.1.1 Summary Of Themes

The two themes are as follows:

- 1) To determine whether home EEG characterisation of sleep is sufficient for clinical trials of patients with early AD through testing
- 2) To determine potential utility of blood biomarkers in sleep and dementia research

#### 2.1.2 Primary Objectives

### Theme 1

2.1.2.1 Feasibility of home high-density EEG (primary objective);

2.1.2.2 Acceptability of home EEG;

#### Theme 2

2.1.2.3 Feasibility of blood biomarkers for AD;

### 2.1.3 Secondary Objectives

#### Theme 1

SleepAD Protocol v6.0 6th September 2024

- 2.1.3.1 Sensitivity of home high-density EEG to detect behaviourally relevant sleep neurophysiology
- 2.1.3.2 Feasibility of using concurrent overnight pulse oximetry to screen for obstructive sleep apnoea (OSA)

### Theme 2

- 2.1.3.3 Accuracy of blood biomarkers for AD compared to CSF testing;
- 2.1.3.4 Explore the relationship between blood biomarkers, *APOE* carrier status and sleep metrics in subgroup who have had both.
- 2.1.3.5 Diagnostic sensitivity of blood biomarkers for predicting progression to AD.
- 2.1.3.6 Characterisation of the relationship between CSF orexin and blood biomarkers in predicting sleep-wake disturbance and disease status

### 2.2 Hypotheses

### 2.2.1 Primary Hypotheses:

### Theme 1

Home high-density EEG are feasible and acceptable in people with MCI and AD

### Theme 2

• Blood biomarkers are feasible and acceptable in people with MCI and AD.

### 2.2.2 Secondary Hypotheses:

#### Theme 1

- Home high-density EEG will capture behaviourally relevant sleep metrics
- Concurrent pulse oximetry testing will capture accurate data to enable screening for OSA

### Theme 2

- Blood biomarkers are accurate compared to CSF biomarkers for AD
- Blood biomarkers will show acceptable diagnostic sensitivity, which is further improved when combined with other clinical and demographic information.
- Blood biomarkers of AD pathology will correlate with sleep abnormalities in the pattern suggested by CSF.
- APOE carrier status will correlate with both sleep abnormalities and blood biomarkers of AD pathology
- Distinct sleep characteristics will be detectable in those with blood biomarkers of AD pathology and *APOE* carrier status.
- CSF orexin levels will have a statistically significant positive correlation with blood biomarker levels of amyloid beta and p-tau.

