#### Data analysis will:

- a) Quantify the proportion of lost/degraded blood samples, and data completeness for memory tests
- b) Calculate diagnostic accuracy of the separate index tests (NFL, p-tau) for AD, at prepublished thresholds, compared to reference standard (CSF), via AUROC curves[65]
  - and explore heterogeneity in diagnostic accuracy of index tests AD by prespecified factors listed using cut offs for AD | no AD extrapolated from UCL clinical laboratories.
- Quantify the relationship between p-tau, NFL and sleep metrics in patients who have had both blood biomarkers and high-density EEG
- d) As a post hoc analysis, we will explore the diagnostic accuracy of Montreal Cognitive Assessment (MoCA) as a standard clinical test and visually compare accuracy of NFL and tau to that of MoCA.
- e) Where CSF is available, we will run biomarker analyses on the UCL research SIMOA machine to internally validate samples also tested as part of routine clinical care on the UCL clinical laboratory SIMOA machine.
- f) Once longitudinal data has been collected from our pre-clinical/MCI cohort, we will calculate the diagnostic accuracy of the separate index tests for AD via AUROC curves. The relationship between conversion to AD and the index tests will be assessed using regression models with age, sex, baseline MoCA score, plasma: CSF orexin ratio, and baseline APOE carrier status as covariables.

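### Section 10.2 gives AUROCs for single tests and an adjusted association with conversion, so it does not test the hypothesised gain in accuracy from combining markers with clinical information

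*Protocol*

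**What the plan says.** The relevant statements are spread over four parts of the protocol.

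- **Hypothesis (2.2.2, Theme 2):** "Blood biomarkers will show acceptable diagnostic sensitivity, which is further improved when combined with other clinical and demographic information". Its wording matches objective 2.1.3.5, "Diagnostic sensitivity of blood biomarkers for predicting progression to AD". Accuracy against CSF has its own objective (2.1.3.3) and its own hypothesis, which does not mention combination.
- **Background (1.1, Accuracy):** the authors commit to modelling how biomarkers improve dementia risk prediction once joined with baseline demographic and clinical information.
- **Cross-sectional analysis (10.2, Substudy 2, item b):** "Calculate diagnostic accuracy of the separate index tests (NFL, p-tau) for AD", against CSF. Item d) takes MoCA on its own and compares it with the markers by eye.
- **Longitudinal analysis (10.2, Substudy 2, item f):** "we will calculate the diagnostic accuracy of the separate index tests for AD via AUROC curves". Then: "The relationship between conversion to AD and the index tests will be assessed using regression models", specified as "regression models with age, sex, baseline MoCA score, plasma: CSF orexin ratio, and baseline APOE carrier status as covariables".

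**The concern.** The hypothesis has two parts: that sensitivity is acceptable, and that it rises when clinical and demographic information is added. The single-test AUROCs address the first part. The second needs the accuracy of a combined rule and its difference from the marker alone. No item in 10.2 yields either quantity, and 10.2 specifies the accuracy target twice as separate tests.

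The regression in f) is the only analysis that puts markers and clinical variables in one model. Followed literally, it delivers coefficients. If a marker stays significant after adjustment, the natural but wrong conclusion is that the combination has been shown to be more accurate. The trial would then report on a stated hypothesis without having measured the quantity it concerns.

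**Working it through.** **1. What each planned output can answer.**

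| Output in 10.2 | Combined accuracy? | Gain over marker alone? | Gain over clinical data alone? |
|---|---|---|---|
| b) AUROC of each marker v CSF | no | no | no |
| d) AUROC of MoCA, visual comparison | no | no | no |
| f) AUROC of each marker v conversion | no | no | no |
| f) regression with covariables | model fitted, no accuracy measure named | not named | not named |

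**2. The comparators differ.** Section 2.2.2 starts from the markers and asks what clinical information adds. Section 1.1 starts from clinical information and asks what the markers add. These are two different differences, and 10.2 specifies neither.

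**3. Why an adjusted association is not a gain in accuracy.** Illustrative binormal model, all inputs assumed except 0.80, which is the AUROC that 1.1 cites for P-tau 181 alone. Let the marker have AUROC 0.80 and a single clinical score have AUROC 0.65, 0.70 or 0.75, with within-group correlation ρ.

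- Separation: d = √2 × Φ⁻¹(AUROC). Marker d₁ = 1.190; clinical score d₂ = 0.545, 0.742 or 0.954.
- Combined: D² = (d₁² + d₂² − 2ρd₁d₂)/(1 − ρ²); combined AUROC = Φ(D/√2).
- Adjusted log odds ratio of the marker per SD: (d₁ − ρd₂)/(1 − ρ²).

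| ρ | Clinical AUROC | Adjusted OR for marker | Combined AUROC | Gain over marker alone |
|---|---|---|---|---|
| 0 | 0.65 | exp(1.190) = 3.29 | 0.823 | 0.023 |
| 0 | 0.70 | 3.29 | 0.839 | 0.039 |
| 0 | 0.75 | 3.29 | 0.860 | 0.060 |
| 0.3 | 0.65 | exp(1.128) = 3.09 | 0.803 | 0.003 |
| 0.3 | 0.70 | exp(1.063) = 2.90 | 0.813 | 0.013 |
| 0.3 | 0.75 | exp(0.993) = 2.70 | 0.829 | 0.029 |

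An identical odds ratio goes with gains of 0.023, 0.039 and 0.060. An odds ratio of 3.09 goes with almost no gain. The coefficient that f) would report does not determine the quantity in the hypothesis.

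**4. The plan's own precision figure.** Sections 4.4 and 10.1 give N = 100, a margin of 0.08, AUROC 0.9 and 50% prevalence. With 50 cases and 50 non-cases at 95%, the upper-bound variance gives 1.96 × √(0.9 × 0.1/50) = 0.083, which rounds to 0.08. The Hanley-McNeil variance gives 1.96 × 0.0321 = 0.063. The protocol names neither the method nor the confidence level. On either reading the figure concerns one AUROC and says nothing about a difference.

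**5. Precision of a paired difference.** Assume a gain from 0.80 to 0.88. Section 1.1 cites both values, the second as "the combination of NFL and P-tau 181 has an AUROC of 0.88 compared to delayed verification of AD", but they rest on different reference standards, so 0.08 is only an assumed gain. SE of the difference = √(s₁² + s₂² − 2r·s₁s₂), with Hanley-McNeil s₁ and s₂ and an assumed correlation r of 0.3 to 0.7 between the AUROCs.

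| Setting | s₁, s₂ | SE of difference (r = 0.3; 0.7) | 95% half-width | Power, two-sided 5% |
|---|---|---|---|---|
| 100 participants, 50 cases | 0.0445, 0.0351 | 0.0477; 0.0320 | 0.094; 0.063 | 38.9%; 70.5% |
| 50 participants, 15 converters | 0.0750, 0.0609 | 0.0812; 0.0542 | 0.159; 0.106 | 16.5%; 31.4% |

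The second row assumes 50 pre-clinical/MCI participants and 30% converting, because the protocol gives neither number. With 15 converters, five covariables and one marker, there are 15/6 = 2.5 events per coefficient. An apparent AUROC from that model would be clearly optimistic.

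**The case against.** The strongest reply is that the combined analysis is planned. Section 1.1 commits to it, and the regression in f) holds the markers together with age, sex, MoCA, orexin ratio and APOE. Fitted probabilities from that model would give an AUROC directly. The choice of performance measure, optimism correction and interval is commonly left to a statistical analysis plan, which may exist.

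Much of this stands. A reader might infer that no combined analysis is planned at all; the documents do not support that, for the reasons just given. The absence of a named bootstrap or interval method is not the defect either. What remains is that 10.2 specifies the accuracy target twice as separate tests and gives the combined model a different target. An analysis plan that followed 10.2 faithfully would leave out the hypothesised quantity.

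Two other stronger readings also fail.

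- A reader might infer that scoring NFL alone is an error, since 1.1 describes "neurofilament light chain (NFL, marker of all-cause neurodegeneration" and cites it in combination with P-tau 181. An AUROC for a single index test is legitimate, the protocol does not call NFL unsuitable, and no hypothesis concerns NFL plus p-tau.
- A reader might infer that item b) is deficient. It answers the separate CSF hypothesis as that is written.

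The objection that the data may be too few to settle the question is fair. It affects how the result should be labelled, and it does not make an adjusted coefficient a better answer.

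**Conclusion.** The point holds in a limited form. The protocol hypothesises an improvement in sensitivity on combination and promises to model such an improvement, but the analyses listed in 10.2 do not measure it, and 1.1 and 2.2.2 imply different comparators. The consequence is confined to one secondary hypothesis; the feasibility objectives and the CSF accuracy analysis are unaffected.

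The size of the gain cannot be derived from the documents. Under the assumed binormal inputs it runs from 0.003 to 0.060 in AUROC over the marker alone, and the adjusted odds ratio does not tell these cases apart. If the gain is estimated among converters, the 95% half-width is about 0.11 to 0.16 under the assumed 50 participants and 30% conversion. The study can estimate the improvement but is unlikely to confirm it. The change is worth making and is not critical.

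**What to change.** In 10.2 f), keep the separate-test AUROCs and add the following, all computed in the same participants:

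- Bootstrap optimism-corrected AUROC, and sensitivity at a specificity fixed in advance, for (i) the blood marker or markers alone, (ii) the clinical and demographic model alone, and (iii) the two combined.
- The paired differences (iii) − (i), which answers 2.2.2, and (iii) − (ii), which answers 1.1, each with a 95% CI.
- A statement of which of the listed covariables count as clinical and demographic, and of which markers enter.
- A statement that these are estimates and not confirmatory tests, because converters will be few.

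Using the same participants matters because 6.3 makes the APOE analysis and the extra CSF optional in Substudy 2. A combined model that needs both may be fitted in fewer people than the marker-alone AUROC. Applying the same combined score against CSF status in b) is optional.

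The cost is some wording and a few extra model fits on data already planned. The drawbacks are more estimates to report, wide intervals, and corrected figures slightly less favourable than the apparent ones.
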